The study will produce scientifically strong evidence as to whether two alternative models of community HIV screening among FSW (assisted and unassisted) result in (1) increased rates of formal HIV testing at health facilities and (2) increased rates of treatment initiation in districts in which the community screening intervention is added to the existing FSW community outreach model.

Two alternative study protocols are described in this document. The bulk of this document presents a protocol for a community randomized controlled trial (cRCT), which is the preferred research design option. However, due to a delay in procurement of the OraQuick® rapid HIV test kits that are to be used in the study, there may be insufficient time to undertake a full cRCT.¹ Accordingly, a contingency protocol that can be implemented in a shorter period of time is also presented.

6. Study Objectives

The primary objectives of this study will provide answers to the following five (5) questions:

1. Does the proportion of FSW who know their HIV status increased?

¹ All research activities must be completed by 31 December 2020.

2. Does the introduction of community HIV screening among FSW increase the rate of HIV testing at health facilities?
3. Does “assisted” or “unassisted” community HIV screening among FSW result in a larger increase in the rate of HIV testing at health facilities?
4. Does “assisted” and “unassisted” community HIV screening among FSW results in a larger increase in the rate of HIV positive case finding?
5. Does the introduction of community HIV screening among FSW increase the rate of initiation of ART?

The secondary objectives of this study will provide answers to the following two (2) questions:

1. What is the acceptability of community-based self-screening for FSWs participating in this study?
2. What is the satisfaction of FSWs participating in this study towards delivery of community-based self-screening?

B. STUDY DESIGN

1. Design Summary

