The flowchart of the study is presented in Figure 1. Randomization was carried out among the 23 priority districts in this study with a ratio of 2:1 (that is, 2 intervention districts per 1 control district). The details of randomization are explained in section B.4 of this document. **The assigned 15 intervention districts and 8 comparison districts** are described in Table 6. Potential participants in the intervention area will be screened through the inclusion and exclusion criteria established for

this study. The criteria for participants who are eligible for this study are explained in section B.3 of this document and Annex2.

According to the Indonesian Ministry of Health's current recommendation, HIV blood test at an authorized health facility is still the current practice for HIV diagnosis. Both participants in the intervention and comparison area will be offered for HIV blood test at a health facility. Participants in comparison areas and participants in intervention areas who agree to take HIV test at a health facility will then be managed further according to the existing guideline or "standard of care." For participants in intervention areas who refuses to have her blood drawn for HIV test at a health facility will then be offered self-testing using OraQuick®. Participants will then fill and sign the informed consent to participate in CBS study.

Next, participants will be offered to do the test assisted or unassisted. If the participant chooses to perform the test assisted, the PL/PE will help her from filling in a baseline survey, performing the test, and filling in a post-test survey. If the participant chooses to perform the test unassisted, there will be two options for the participant to get the test kit. First, PL/PE will deliver the test kit for the participant, help with filling in the baseline survey on the spot and give information about uploading test results and the post-test survey, along with a hotline number to call for any questions and concerns, including follow-up steps after participants have received the results. The second method, participants will be given a link online which will entitle information of this study, eligibility criteria, informed consent, baseline survey, link to order a test kit, link to upload result and link to fill in the post-test survey. Participant who chooses this second method will also be given hotline number should there be any further inquiries.

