18	Kota Malang	3	243	Intervention
19	Kota Tangerang Selatan	1	184	Intervention
20	Kota Bekasi	2	158	Comparison
21	Kota Surakarta	2	144	Intervention
22	Kota Semarang	2	129	Comparison
23	Kab. Deli Serdang	1	80	Intervention

Table 7. Allocated intervention districts

No	Kab/Kota	Region	Achieved target of HIV testing per semester (2018-2019)	Group
1	Kab. Deli Serdang	1	80	Intervention
2	Kota Medan	1	575	Intervention
3	Kota Palembang	1	694	Intervention
4	Kab. Tangerang	1	391	Intervention
5	Kota Tangerang Selatan	1	184	Intervention
6	Kota Jakarta Barat	1	544	Intervention
7	Kota Jakarta Pusat	1	473	Intervention
8	Kota Jakarta Timur	1	479	Intervention
9	Kota Bogor	2	374	Intervention
10	Kota Depok	2	287	Intervention
11	Kota Surakarta	2	144	Intervention
12	Kota Surabaya	3	568	Intervention
13	Kota Malang	3	243	Intervention
14	Kota Denpasar	3	982	Intervention
15	Kota Sorong	4	415	Intervention

Table 8. Allocated comparison districts

No	Kab/Kota	Region	Achieved target of HIV testing per semester (2018-2019)	Group
1	Kota Bandar Lampung	1	319	Comparison
2	Kota Jakarta Utara	1	612	Comparison
3	Kota Jakarta Selatan	1	448	Comparison
4	Kota Bekasi	2	158	Comparison
5	Kota Semarang	2	129	Comparison
6	Kota Bandung	2	487	Comparison
7	Kota Makassar	3	866	Comparison
8	Kota Jayapura	4	323	Comparison

5. Recruitment and Sample Size

All FSW in intervention districts who meet study eligibility criteria will be offered community screening (see Section C below for intervention implementation guidelines). FSW in comparison districts will continue to receive the current standard package of interventions.

In to be able to detect a 10 percentage point difference in the rate of HIV testing at health facilities between FSW in intervention vs. comparison districts and have 95% certainty that a difference of that magnitude would not have occurred by chance and 90% certainty of detecting a difference of this magnitude if the difference was real/”the truth,” the following sample of FSW will be needed in intervention and in comparison districts:³

$$n \geq [Z_{1-\alpha} (2P(1-P))^{1/2} + Z_{1-\beta} (P_1(1-P_1) + P_2(1-P_2)^2 / (P_1-P_2)^2)] * deft$$

Where:

$Z_{1-\alpha}$ = the Z score for the level of statistical confidence, or statistical precision, desired (for 95%, $Z = 1.96$)

$Z_{1-\beta}$ = the Z score for the desired statistical power (for 90% one-sided test, $Z = 1.282$)

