P_1 = the expected population proportion in the comparison group of districts (set = 0.5 – this is the worst-case scenario and will produced a sample size that is adequate irrespective of the actual proportion)

P_2 = the expected population proportion in the intervention group of districts (set = 0.6 – assume minimum effect size to be realized of 10 percentages points)

$$P = (P_1 - P_2) / 2$$

$(P_1 - P_2)$ = the magnitude of comparison-group differences (or change over time) to be detected with the specified level of precision and power (assumed to be +/- 10 percentage points)

deft = design effect to compensate for clustering at the district level (1.5 assumed).

The required sample size is thus $n \geq 635$ per experimental group; ≥ 761 after 20% allowance for lost-to-follow up

³ Source: Lwanga SK and Lemeshow S. Sample Size Determination in Health Studies: A Practical Manual. Geneva: World Health Organization.

Interpretation: we would need to recruit 761 FSW who self-test for HIV testing in the intervention districts and 761 FSW for HIV testing at health facilities in comparison districts to be able to detect a 10 percentage point difference in the rate of HIV testing at health facilities (intervention vs. comparison districts) to have 95% certainty that a difference of that magnitude would not have occurred by chance and 90% certainty of detecting a difference of this magnitude if such a difference existed.

In order to assess whether “assisted” or “unassisted” community HIV screening among FSW results in a larger increase in the rate of HIV testing at health facilities, we would need samples of size $n \geq 761$ each of FSW who received assisted and unassisted screening in intervention districts, a total of $n \geq 1,522$ FSW in intervention districts, plus $n \geq 761$ in comparison districts.

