In the event that participants' data are collected by paper, a procedure to upload the data into the established online system will be developed. Each data manager in the IUs needs to conduct the procedure regularly. This is to ensure that all data are being captured thoroughly.

F. DATA ANALYSES

The data analyses to be undertaken will be directed to addressing the research questions laid out at the beginning of the protocol and statistical tests appropriate to each specific analysis will be performed to inform the interpretation of results. The specific steps in the data analysis will be as follows:

1. Compare the characteristics of FSWs who receive self-testing and blood testing.

2. Compare the characteristics of FSWs who receive assisted and unassisted self-testing.
3. Compare proportion of FSWs taking confirmatory test out of those who receive the test in the assisted and unassisted self-testing.
4. Compare the proportion of FSWs who receive HIV test out of those who got offered for the test (including self-testing) in the intervention group with proportion of FSWs who receive HIV test in the control group.
5. Compare the proportion of FSWs taking confirmatory test (including self-testing) out of those receive the test in intervention groups and control group.
6. Compare the proportion of HIV positive in the assisted, unassisted (intervention) and HIV positive in the control group.
7. Compare the proportion of ART initiation in the assisted, unassisted (intervention) and the control group.
8. Calculate the cascade of HIV testing and treatment.
9. Compare stigma scores and FSWs who went to a health facility for HIV testing between assisted, unassisted group.
10. Compare the HIV and STI risk behaviors between assisted and unassisted group.

G. CONTINGENCY STUDY DESIGN

Should the OraQuick® test kits not become available in sufficient time to conduct a full-scale cRCT, a smaller-scale study will instead be undertaken. The purpose of the smaller study is the same as the cRCT described above, and the same protocol described above will be implemented. But the comparison is achieved targets between before and after intervention – there will be no comparison districts. The study will be undertaken in three (3) districts. The three districts will be selected from different parts of Indonesia, and they are: Kota Bandung (west part of Indonesia), Kota Denpasar (central part of Indonesia), and Kota Makassar (center-east part of Indonesia).

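### No Section F analysis compares health-facility HIV testing between intervention and comparison districts, the outcome of Objective 2 and of the sample-size calculation

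*Combined protocol and SAP*

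**What the plan says.** Section A.6, question 2, asks: "Does the introduction of community HIV screening among FSW increase the rate of HIV testing at health facilities". Section A.5 puts the same outcome first among what the study should show: "increased rates of formal HIV testing at health facilities and (2) increased rates of treatment initiation in districts in which" community screening is added. Section B.5 sizes the trial to "detect a 10 percentage point difference in the rate of HIV testing at health facilities between FSW in intervention vs. comparison districts", with 50% assumed in comparison and 60% in intervention districts.

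Section F opens with a commitment: "The data analyses to be undertaken will be directed to addressing the research questions laid out at the beginning of the protocol". Ten specific steps follow. Item 4 is "Compare the proportion of FSWs who receive HIV test out of those who got offered for the test (including self-testing) in the intervention group", against the proportion tested in the control group. Item 3 is "Compare proportion of FSWs taking confirmatory test out of those who receive the test in the assisted and unassisted self-testing".

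B.5 interprets its result this way: "recruit 761 FSW who self-test for HIV testing in the intervention districts and 761 FSW for HIV testing at health facilities", where the second group belongs to the comparison arm. Section B.1 describes who is offered a kit: "participants in intervention areas who refuses to have her blood drawn for HIV test at a health facility will then be offered self-testing". The table in E.3 records offers, agreement and attendance at a facility in both arms (rows 1 to 4), and kit offers, uptake and results in the intervention arm only (rows 5 to 8). Row 9 records later facility tests, also in the intervention arm only and after reactive screens only.

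**The concern.** The trial is sized for a difference in facility testing by allocated district. A statistician who carried out Section F step by step would never produce that estimate. The between-arm testing result that would be produced is item 4, where a kit used at home counts the same as a blood test at a clinic and only one arm has kits. A gain in any testing could then be taken as the answer to the facility-testing question, although women who self-test need not go on to a facility.

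The sample statement adds to the problem. Women who self-test on the outreach route are those who turned down the facility test. They are a subgroup formed after allocation, not the intervention arm of the powered contrast.

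**Working it through.** **1. The plan's own figure.** Inputs from B.5: P1 = 0.5, P2 = 0.6, power 90% (Z = 1.282), design effect 1.5, 20% allowance. The standard two-proportion formula with mean proportion 0.55 and a one-sided Z of 1.645 gives 423 per group. Then 423 × 1.5 = 634.5 and 634.5 × 1.2 = 761.4, which match the stated 635 and 761. (The printed Z of 1.96 would give 519, 778.5 and 934; that mismatch is a separate matter.) The figure is therefore sized for 50% against 60% facility-tested by arm.

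**2. Section F against that contrast.**

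| Item | What is compared | Facility testing by arm? |
|---|---|---|
| 1, 2, 10 | Characteristics or risk behaviour by test type or route | No |
| 3, 9 | Assisted with unassisted women | No arm contrast |
| 4 | Any test, self-tests included, by arm | Wrong outcome for Objective 2 |
| 5 | Confirmatory tests among women already tested, by arm | Wrong denominator |
| 6, 7 | HIV positivity, ART initiation | No |
| 8 | Testing and treatment cascade | No contrast stated |

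The parenthesis in item 4 could attach to the offer or to the test. The matching item 4 in Section G attaches self-testing to tests received, which supports the reading used here.

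**3. How far item 4 can depart from facility testing.** The documents give no uptake figures, so these inputs are assumptions:
- f = 50% facility-tested at first offer in both arms (the B.5 planning value).
- d = share offered a kit.
- q = self-test uptake among those women.
- l = share of self-testers later tested at a facility.
- Later facility tests among all other women are set to zero in both arms.

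Item 4 difference = d × q. Facility-testing difference = d × q × l. Excess of item 4 = d × q × (1 − l).

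Case A: everyone not facility-tested is offered a kit, d = 1 − 0.5 = 0.5.
- Item 4 reaches +10 at q = 0.10/0.5 = 20%. With l = 0 there is no added facility test.
- q = 50%, l = 20%: item 4 +25, facility +5.
- q = 30–70%, l = 10–50%: item 4 +15 to +35, facility +1.5 to +17.5.

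Case B: kits go to decliners only, 70% agree and 50% attend, d = 1 − 0.7 = 0.3.
- Item 4 reaches +10 at q = 0.10/0.3 = 33%.
- q = 50%, l = 20%: item 4 +15, facility 0.3 × 0.5 × 0.2 = +3.
- Same ranges: item 4 +9 to +21 (0.3 × 0.3; 0.3 × 0.7), facility +0.9 to +10.5 (0.3 × 0.3 × 0.1; 0.3 × 0.7 × 0.5).

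**4. What 761 self-testers mean.** Women offered testing = 761/(d × q). At q = 50% this is 761/0.25 = 3,044 in case A and 761/0.15 = 5,073 in case B. Under either assumption, 761 self-testers are a fraction of the women in the Objective 2 denominator.

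**The case against.** The strongest reply concerns item 5. Section B.1 makes the confirmatory test a facility blood test, and the contingency version of item 5 in Section G drops the restriction to women already tested and sets intervention confirmatory tests against control HIV tests. On that reading the contrast is present but badly worded. This stands in part, since item 5 is the nearest thing to the missing analysis. But the contingency wording still leaves out intervention women who accepted the facility test at first offer, because they have no screen to confirm. It therefore compares part of one arm with the whole of the other.

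B.5 also recommends measuring impact with SIHA data in both groups of districts. That sentence belongs to the paragraph on treatment eligibility and is not carried into Section F.

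Item 4 is not wrong in itself. It fits Objective 1 and the testing-coverage aim in B.1, and nothing in the plan says it will be presented as the answer to Objective 2.

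The size of the gap depends on who gets a kit. Women who agree to a facility test but do not attend are not offered one, so case A tends to run high. That is why case B is shown.

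A reader might also infer that the plan cannot capture facility tests after non-reactive assisted screens. The documents do not establish this. The E.3 table omits them, but referral cards are offered to these women, C.5 pays facilities for confirmatory-test data on both routes, item 3 needs such data, and the Annex 1 flowchart is not visible.

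**Conclusion.** The point holds. Following Section F as written leaves Objective 2, the between-arm question for which the trial is sized, without an estimate. The general commitment to address the research questions does not supply one, because the specific steps omit it.

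The omission itself rests on the text alone. The figures are illustrations. Item 4 can reach 10 points with no added facility test at an uptake of 20% among all women not facility-tested, or 33% among decliners if 70% agree and 50% attend. Both assume 50% facility-tested at first offer in both arms.

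A reader might infer that item 4 could show a gain while facility testing falls. That would require the self-test offer also to lower first-offer acceptance of the facility test, and the documents give no evidence of this. With equal first-offer testing, and later tests among the other women equal in both arms, the facility-testing difference cannot be negative.

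Two limits remain after any correction. Objective 2 names no denominator, and who is reached and offered testing is settled after allocation and may differ by arm.

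**What to change.** - Add a Section F item for Objective 2: the proportion with a facility HIV blood test during the study among eligible women offered testing through outreach (E.3 rows 1 and 2), by allocated district.
- Count row 4 plus later facility tests, ascertained in the same way in both arms. Extend row 9 to all screen results on both routes. Record later facility tests among initial decliners in comparison districts and among unscreened decliners in intervention districts. Counting later tests only after self-screening would favour the intervention arm.
- State one rule, for both arms, on whether mobile-clinic tests count. Section C.4 allows them in control districts.
- Keep item 4 and assign it to Objective 1.
- Reword the B.5 interpretation so that the Objective 2 sample is women offered testing per arm. Give the self-tester numbers (761 + 761 = 1,522) as a separate target for Objective 3.
- Report the numbers and characteristics of women offered testing by arm, and state whether women recruited through the online link are included.

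The cost is one analysis item, a small number of extra recording fields in both arms, and reworded sample text. Rows 1 to 4 are already recorded in both arms. The sponsor should expect a facility-testing effect that is likely smaller than the any-test contrast.

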Participants with reactive or indeterminate result resulting from either assisted or unassisted methods will be encouraged to get a confirmatory test at a health facility. A confirmatory test will also be suggested for participants with non-reactive result. The difference between these two result groups will be the level of encouragement given to do the confirmatory test. While participant with reactive or indeterminate results will be strongly encouraged, participants with a non-reactive result will be suggested for a confirmatory test. These suggestions are derived from Indonesia's current guideline on HIV detection, where the confirmatory test is to be done at the health facility using the HIV blood test.

Figure 1. Study Flowchart

[figure not shown]

Table 3. Global Fund HIV testing targets in 23 districts for 2019-2020

No	Province	Districts	Region	Target of HIV Testing			
				P3	P4	P5	P6
1	Sumatera Utara	Kota Medan	1	904	904	1,002	1,002
2	Sumatera Utara	Kab. Deli Serdang	1	406	406	450	450
3	Sumatera Selatan	Kota Palembang	1	1,371	1,371	1,520	1,520
4	Lampung	Kota Bandar Lampung	1	393	393	435	435
5	Banten	Kota Tangerang Selatan	1	223	223	247	247
6	Banten	Kab. Tangerang	1	820	820	909	909
7	DKI Jakarta	Kota Jakarta Selatan	1	536	536	594	594
8	DKI Jakarta	Kota Jakarta Timur	1	877	877	973	973
9	DKI Jakarta	Kota Jakarta Pusat	1	1,341	1,341	1,486	1,486
10	DKI Jakarta	Kota Jakarta Barat	1	1,318	1,318	1,461	1,461
11	DKI Jakarta	Kota Jakarta Utara	1	1,431	1,431	1,586	1,586
12	Jawa Barat	Kota Bogor	2	474	474	525	525
13	Jawa Barat	Kota Bekasi	2	248	248	275	275
14	Jawa Barat	Kota Bandung	2	582	582	645	645
15	Jawa Barat	Kota Depok	2	374	374	415	415
16	Jawa Tengah	Kota Semarang	2	510	510	565	565
17	Jawa Tengah	Kota Surakarta	2	172	172	190	190
18	Jawa Timur	Kota Malang	3	84	84	93	93
19	Jawa Timur	Kota Surabaya	3	1,173	1,173	1,300	1,300
20	Bali	Kota Denpasar	3	1,407	1,407	1,559	1,559
21	Sulawesi Selatan	Kota Makassar	3	1,444	1,444	1,600	1,601
22	Papua Barat	Kota Sorong	4	438	438	485	485
23	Papua	Kota Jayapura	4	786	786	871	871

Table 4. Achieved target of HIV testing per semester in 23 priority districts (2018-2019)

No	Kab/Kota	Region	Achieved target of HIV testing per semester
1	Kota Denpasar	3	982
2	Kota Makassar	3	866
3	Kota Palembang	1	694
4	Kota Jakarta Utara	1	612
5	Kota Medan	1	575
6	Kota Surabaya	3	568
7	Kota Jakarta Barat	1	544
8	Kota Bandung	2	487
9	Kota Jakarta Timur	1	479
10	Kota Jakarta Pusat	1	473
11	Kota Jakarta Selatan	1	448
12	Kota Sorong	4	415

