13	Kab. Tangerang	1	391
14	Kota Bogor	2	374
15	Kota Jayapura	4	323
16	Kota Bandar Lampung	1	319
17	Kota Depok	2	287
18	Kota Malang	3	243
19	Kota Tangerang Selatan	1	184
20	Kota Bekasi	2	158
21	Kota Surakarta	2	144
22	Kota Semarang	2	129
23	Kab. Deli Serdang	1	80

Table 5. Achieved target of outreach per year in 23 priority districts (2018-2019)

No.	Kab/Kota	Region	Achieved target of outreach per year
1	Kota Denpasar	3	5100
2	Kota Jakarta Barat	1	4947
3	Kota Jakarta Pusat	1	4004
4	Kota Palembang	1	3741
5	Kota Surabaya	3	3510
6	Kota Jakarta Timur	1	3157
7	Kota Jakarta Utara	1	3129
8	Kota Jakarta Selatan	1	2905
9	Kota Medan	1	2858
10	Kota Makassar	3	2683
11	Kota Bandung	2	2164
12	Kota Bogor	2	1961
13	Kota Bandar Lampung	1	1933
14	Kabupaten Tangerang	1	1374
15	Kota Semarang	2	1317
16	Kota Sorong	4	1220
17	Kota Surakarta	2	1190
18	Kota Depok	2	1107
19	Kota Tangerang Selatan	1	994
20	Kota Jayapura	4	983
21	Kabupaten Deli Serdang	1	939
22	Kota Bekasi	2	879
23	Kota Malang	3	877

2. Study Period

The study timeline is presented below. The study will be conducted from February 2020 to November 2020 (10 months). The preparatory activities will be conducted in February to March 2020. **The intervention will be implemented from April – October 2020 (7 months)**, with the last one months of 2020 allocated for data analysis, report writing and a workshop presenting study findings.

Study timeline

Activities	Month									
	Feb	March	April	May	June	July	Aug	Sept	Oct	Nov
1. Study preparation										

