3.1 Study kick-off										
3.2 Data collection										
4. Data analysis and report writing										
5. Workshop for study finding dissemination										

3. Eligibility Criteria

The target audience for the intervention to be evaluated are FSW in Intervention districts that meet the criteria outlined below.

Inclusion criteria

- Women, 18 years or older at enrolment
- Reports transactional sex (vaginal, oral and/or anal) at least once in the past month
- No HIV test in last 6 months
- Self-reported HIV negative OR HIV status unknown

Exclusion criteria

- Unwilling to participate for any reason
- Concurrently participating in another HIV prevention study

4. Randomization

Stratified randomization was carried out for the 23 priority districts involved in this study. First, sampling strata were created by sorting the mean average value of achieved HIV testing target per semester from 2018-2019 in each district from the largest to the smallest. The second step was to sort the districts into eight groups of three districts, except for the last group which will only consist of two districts. Randomization for intervention and comparison group were then carried out within these groups of eight with 2:1 ratio (2 intervention: 1 comparison).² The results of stratified randomization are presented in Table 6. In separate table, Table 7 contains 15 intervention districts and Table 8 contains 8 comparison districts.

² A 2-to-1 intervention to comparison district ratio was chosen in order to increase the likelihood of recruiting a sufficient number of FSW for community screening to reach the sample size target considering the relatively short time frame available for for study implementation.

Table 6. Allocated intervention group and comparison group

No	Kab/Kota	Region	Achieved target of HIV testing per semester (2018-2019)	Group
1	Kota Denpasar	3	982	Intervention
2	Kota Makassar	3	866	Comparison
3	Kota Palembang	1	694	Intervention
4	Kota Jakarta Utara	1	612	Comparison
5	Kota Medan	1	575	Intervention
6	Kota Surabaya	3	568	Intervention
7	Kota Jakarta Barat	1	544	Intervention
8	Kota Bandung	2	487	Comparison
9	Kota Jakarta Timur	1	479	Intervention
10	Kota Jakarta Pusat	1	473	Intervention
11	Kota Jakarta Selatan	1	448	Comparison
12	Kota Sorong	4	415	Intervention
13	Kab. Tangerang	1	391	Intervention
14	Kota Bogor	2	374	Intervention
15	Kota Jayapura	4	323	Comparison
16	Kota Bandar Lampung	1	319	Comparison
17	Kota Depok	2	287	Intervention

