Sample size requirements for the third question measurement pertains to the number of FSW who test positive for HIV at a health facility and are thus eligible to initiate treatment. This will depend upon (1) the number of FSW presenting at health facilities for testing and (2) the positivity rate among those tested. Sample sizes should thus be calculated accordingly. If we assume a testing positivity rate of 3%, it is apparent that the expected number of FSWs who would be eligible for treatment will be small and we will lack sufficient statistical power to make meaningful comparisons with comparison districts. For this reason, it is recommended that the impact of community screening among FSW be measured using SIHA data for FSW in both intervention and comparison districts. This estimate of impact derived in this way will be confounded if it were to be the case that interventions other than HIV self-testing were to be better implemented in intervention vs. comparison districts. It might be possible to minimize this potential bias by including measures of intervention implementation performance in the intervention and comparison districts in multivariable analyses. Thus, a large enough sample size is required to ensure sufficient power to determine the difference in the intervention and control districts.

C. THE INTERVENTION

1. General Description of The Intervention

FSW who meet the eligibility criteria will be offered for HIV blood test first. Participants who wish to take the test will then managed according to the current guideline for standard of care. Participants who disagree to take HIV blood test will then be offered screening test with Ora-Quick®. There will be with two options for community HIV screening by Peer Leaders: (1) in a convenient community setting assisted by PL/PE (assisted screening) or (2) in a setting of their own choosing without assistance from PL/PE (unassisted screening). FSW will also be able to access a community-based screening test by following online link from messages spread through WhatsApp number without having to come into contact with outreach workers. The saliva-based Ora-Quick® test kit will be used for community screening.

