The primary limitations of the smaller-scale study are (1) the districts were not randomly chosen and (2) the proportion of HIV testing before and after intervention that might not sufficient to produce a statistically significant result to prove the success of the intervention. This smaller-scale version of the study should be viewed as a demonstration or pilot project leading to a bigger study afterwards.

Data analysis will be done by comparing changes in outcome variables measured against results in the four semesters prior to the study in the 3 districts compared to the other 20 acceleration districts.

Analysis of outcome variables are similar with the cRCT approach as below:

1. Compare the characteristics of FSWs who receive self-testing and blood testing in 3 districts.
2. Compare the characteristics of FSWs who receive assisted and unassisted self-testing 3 districts.
3. Compare proportion of FSWs taking confirmatory test in the assisted and unassisted self-testing 3 districts.

4. Compare the proportion of FSWs who receive HIV test including self-testing in the intervention group with proportion of FSW who receive HIV test in the control group (in 3 districts before the intervention and other 20 acceleration districts).
5. Compare the proportion of FSWs taking confirmatory test (including self-testing) in the intervention group with proportion of FSW who receive HIV test in the control group (in 3 districts before the intervention and the other 20 acceleration districts).
6. Compare the proportion of HIV positive in 3 districts (assisted and unassisted) and HIV positive in the control group (in 3 districts before the intervention and other 20 acceleration districts).
7. Compare the proportion of ART initiation in 3 districts (assisted and unassisted) and the control group (in 3 districts before the intervention and other 20 acceleration districts).
8. Calculate the cascade of HIV testing and treatment.
9. Compare stigma scores and FSW who went to a health facility for HIV testing.
10. Compare the HIV and STI risk behaviors.

H. RESEARCH ETHICS AND PERMISSION

[figure not shown]

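### The cRCT comparison of testing rates uses neither the eight randomisation groups nor the districts' 2018-2019 testing rates, which costs precision and leaves chance imbalance uncorrected

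*Combined protocol and SAP*

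**What the plan says.** Objective 2 (section A.6) asks: "Does the introduction of community HIV screening among FSW increase the rate of HIV testing at health facilities". Section F item 4 compares the proportion tested among women offered a test "in the intervention group with proportion of FSWs who receive HIV test in the control group", counting self-tests in the intervention arm. Items 5 to 7 have the same between-group form. None names a pre-trial value or the randomisation groups.

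Section B.4 formed those groups by "sorting the mean average value of achieved HIV testing target per semester from 2018-2019 in each district from the largest to the smallest" and allocated 2:1 within each. The sorting variable is a number of tests. The sample-size calculation (B.5) is for a rate: 50% against 60%, a 10-point difference.

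Pre-trial data appear in two other places. Table 4 gives each district's tests per semester and Table 5 its outreach contacts per year, both for 2018-2019. The non-randomised fallback (section G) is to be analysed by "comparing changes in outcome variables measured against results in the four semesters prior to the study". The only adjustment mentioned for the cRCT, in the B.5 paragraph on treatment initiation and SIHA data, is "including measures of intervention implementation performance in the intervention and comparison districts in multivariable analyses". That is not the prior testing level.

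**The concern.** With 23 districts, and only eight in the smaller arm, randomisation does not reliably even out a rate that varies widely between districts. Balancing test counts does little for the rate if the two are weakly related. An analysis that ignores both the grouping and the starting rate leaves the stable part of the between-district spread in the error. Any chance difference in starting rates also stays in the estimate. With a 10-point target, a few points either way could decide how the result is read. The allocation is already fixed in Table 6, so the analysis is the only place left to deal with this.

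**Working it through.** **The plan's own figures.** The plan states no pre-trial rate by arm, so there is none to reproduce. Its 635 per group for 50% against 60% at 90% power reproduces as a one-sided 5% calculation: 423 x 1.5 = 634.5. Only the 10-point target is used below.

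**Inputs.** Tests per semester (Table 4), outreach per year (Table 5), arm and order (Table 6; consecutive threes, with a final pair, form the groups). Proxy rate = 2 x Table 4 / Table 5. The doubling assumes that two semesters' tests add up to a year. Outreach is treated as a rough head-count because C.4 sets one outreach contact per woman per year.

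**Spread and grouping.** The 23 rates run from 17.0% (Deli Serdang) to 68.0% (Sorong), SD 14.8 points. Their correlation with the test count is 0.24.

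**Chance gap under the plan's scheme.** Seven groups of three and one pair give 3^7 x 2 = 4,374 possible allocations. Enumerating all of them, the gap in proxy rate between arms has an SD of 5.8 points (district means) or 5.7 (pooled). Ignoring the grouping, the standard error is 14.8 x sqrt(1/15 + 1/8) = 6.5. Grouping on counts therefore removed little.

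**Gap in the actual allocation.**
- Pooled: 2 x 6,433 / 36,979 = 34.8% against 2 x 3,342 / 15,993 = 41.8%, a gap of -7.0.
- Mean of district rates: 38.2% against 41.7%, a gap of -3.5.
- Median: 37.1% against 37.5%, a gap of -0.4.
- Permutation p over the 4,374 allocations: 0.20 pooled, 0.42 for means.
- Test counts, the variable that was grouped on: mean 429 against 418.

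**By randomisation group (%).**

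| Group | Intervention | Comparison | Difference |
|---|---|---|---|
| 1 | 38.5, 37.1 | 64.6 (Makassar) | -26.7 |
| 2 | 40.2, 32.4 | 39.1 | -2.8 |
| 3 | 22.0, 30.3 | 45.0 | -18.8 |
| 4 | 23.6, 68.0 | 30.8 | +15.0 |
| 5 | 56.9, 38.1 | 65.7 (Jayapura) | -18.2 |
| 6 | 51.9, 55.4 | 33.0 | +20.6 |
| 7 | 37.0, 24.2 | 35.9 | -5.3 |
| 8 | 17.0 | 19.6 | -2.6 |

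Six of eight differences are negative. The group-adjusted gap is -4.9 (95% CI -17.8 to +7.9).

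**Sensitivity.**
- Without Makassar: comparison pooled 4,952 / 13,310 = 37.2%, gap -2.4; by means -0.3.
- Without Jayapura: comparison pooled 6,038 / 15,010 = 40.2%, gap -5.4; by means -0.1.
- Tests against the first-period (P3) target in Table 3, pooled: 56.5% against 56.4%, no gap.
- Without doubling, all tests-per-contact figures halve: gap 3.5 pooled or 1.8 by means, allocation SD about 2.9.

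**The case against.** A reader might infer that intervention districts demonstrably start 3.5 to 7 points behind, so that the trial is biased against the intervention and a true 10-point gain would show as 6.5 or 3.0. The documents do not support this.

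- **Randomisation.** Allocation was random within groups, so there is no systematic push against the intervention. Over the 4,374 allocations the average unadjusted gap is +1.3 points by district means and +0.3 pooled. It is not exactly zero because the last group is split 1:1, and it slightly favours the intervention.
- **Proxy.** Item 4 concerns women offered a test, and the routine recording table (E.3) restricts to those at least six months from their last one. Table 5 counts all outreach contacts. Under C.4 a woman can be counted as tested in each semester, and at a mobile clinic as well as a facility. The ratio is neither a proportion of women nor a clean baseline for facility testing.
- **Carry-over.** The 6.5 and 3.0 figures need the proxy gap to pass in full into a different outcome and denominator. The documents give no evidence on that.
- **Wording.** In a randomised trial an increase can mean relative to control, and section B.1 describes comparison with control districts. The fallback looks at change over time because it has no randomised comparison districts. Neither is an inconsistency.

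All of this stands, as does the fragility of the observed gap. It does not answer the precision argument, which rests on the spread between districts and not on the direction of this one draw. Section F's general promise of suitable statistical tests does not commit to using the groups or a baseline.

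**Conclusion.** The point holds as one about precision and chance imbalance. For item 4 and the Objective 2 comparison the plan leaves out the grouping it randomised within and a pre-trial rate that it prints for every district. On the proxy, an allocation made the plan's way produces a chance gap with an SD of about 6 points, against the 10 sought. The observed gap of 7.0 pooled or 3.5 by means is compatible with chance and should not be presented as an established deficit.

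The size rests on three assumptions: doubling the semester count, treating outreach contacts as a head-count, and some persistence of district rates into April-October 2020. If persistence is weak, adjustment gains little. The doubling affects the stated size but not the adjustment, since a constant multiple of a covariate changes nothing.

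**What to change.** For item 4 and the facility-testing comparison under Objective 2, prespecify a district-level analysis of the April-October 2020 rate. It should account for the eight randomisation groups and adjust for the district's 2018-2019 tests per outreach contact from Tables 4 and 5. Tabulate that pre-trial rate by arm in the report. Write this in before outcomes are seen, so that the adjustment cannot look chosen after the fact.

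Do not use this baseline for item 5: its outcome is confirmatory testing among women already tested, and Tables 4 and 5 hold no pre-trial counterpart. Where SIHA is the outcome source, adjust for pre-trial SIHA figures only if they exist; the protocol does not show that they do.

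The cost is analysis wording and no new data collection for these two comparisons. With groups as fixed effects, the residual degrees of freedom are 23 - 8 - 1 - 1 = 13, against 23 - 2 = 21 for an unadjusted two-arm district comparison: seven for the groups and one for the covariate.
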